- b) Using (or having their partner use) a highly effective method of contraception during heterosexual activity. Highly effective methods of contraception are⁵:
 - an intrauterine device
 - vasectomy of a female patient's male partner
 - a contraceptive rod implanted into the skin.
 - any combination of hormonal contraceptive and a barrier method (diaphragm with spermicide, cervical cap with spermicide, contraceptive sponge, male condom or female condom)

¹ Women who are defined as not being of childbearing potential are: any female who is postmenopausal (age \geq 55 years with cessation of menses for 12 or more months, or less than 55 years but without spontaneous menses for at least 2 years, or less than 55 years with spontaneous menses during the last 1 year but currently amenorrhoeic, e.g., spontaneous or secondary to hysterectomy, AND with postmenopausal gonadotropin levels (luteinizing hormone and follicle-stimulating hormone levels $<$ 40 IU/L), or postmenopausal estradiol levels ($<$ 5 ng/L) or according to the definition of "postmenopausal range" for the laboratory involved), or who have had a hysterectomy, bilateral salpingectomy, or bilateral oophorectomy.

² Spurious positive serum beta-hCG values may be caused by the underlying urothelial cancer; plausibility of pregnancy should be established for women of childbearing potential with urothelial cancer and positive serum beta-hCG values.

³ Postmenopausal is defined as at least 12 months with no menses without an alternative medical cause; in women $<$ 45 years of age a high follicle stimulating hormone (FSH) level in the postmenopausal range may be used to confirm a post-menopausal state in women not using hormonal contraception or hormonal replacement therapy. In the absence of 12 months of amenorrhea, a single FSH measurement is not sufficient.

⁴ Abstinence (relative to heterosexual activity) can be used as the sole method of contraception if it is consistently employed as the patient's preferred and usual lifestyle and if it is employed during the entire period of risk associated with the study treatment and if it is considered highly effective by local regulatory agencies and ERCs/IRBs. Periodic abstinence (e.g., calendar, ovulation, sympto-thermal, post-ovulation methods, etc.) and withdrawal are not highly effective methods of contraception.

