20. History of additional malignancy that is progressing or requires active treatment. Exceptions include basal cell carcinoma of the skin, squamous cell carcinoma of the skin that has undergone potentially curative therapy, or *in situ* cervical cancer.

Note: An incidental finding of prostate cancer (identified upon resection of the prostate) is acceptable, provided that the following criteria are met: Stage T2N0M0 or lower; Gleason score ≤ 6 , and prostate-specific antigen below lower limit of normal by local laboratory.

21. Chronic leg ulcers, decubitus ulcers, or unhealed incisions.

General patient disposition

22. Known hypersensitivity or allergy any component of the derazantinib formulation.
23. Unable or unwilling to swallow the complete daily dose of study drug, or contraindicated to receive study drug.
24. Any other uncontrolled intercurrent illness that would unduly increase the risk of toxicity or limit compliance with study requirements, including but not limited to ongoing or active symptomatic infection, uncontrolled diabetes mellitus, or hepatic, renal, respiratory, or psychiatric illness.
25. A history or evidence of psychiatric, substance abuse, or any other clinically significant disorder, condition or disease that, in the opinion of the Investigator or the Sponsor if consulted, would pose a risk to the safety of the patient, or would interfere with the study evaluation, procedures, or completion.
26. Pregnant or breast feeding.

In addition, the following exclusion criteria related to atezolizumab are applicable **only** to patients to be enrolled into **Substudies 3 and 4**:

27. Treatment with systemic corticosteroids (except for steroidal replacement therapy) or other systemic immunosuppressive medications (including but not limited to prednisone, dexamethasone, cyclophosphamide, azathioprine, methotrexate, thalidomide, and anti-tumor necrosis factor agents) within 2 weeks prior to first dose of study drug or anticipated requirement for systemic immunosuppressive medications during the study. Generally, inhaled, intranasal, intraocular, topical, and intra-articular joint injections are allowed.
28. Uncontrolled pleural effusion, pericardial effusion, or ascites requiring recurrent drainage procedures (once monthly or more frequently).
29. History of allogeneic stem cell or solid organ transplantation.

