10. Women of child-bearing potential must have a negative local serum pregnancy test (hCG) at the SV and within 72 hours prior to dosing at C1D1. Subsequently, serum pregnancy testing will be performed prior to study drug dosing on Day 1 of every cycle, at the End of Treatment visit, and serum or urine pregnancy testing will be performed monthly for 150 days (5 months) following the last administration of study treatment. Monthly pregnancy testing after the end of treatment may be performed by the patient's local gynecologist to reduce the burden related to study visits at the site, but must be communicated to the study Investigator.
11. Research liquid biopsies are requested from all patients enrolled in **Substudies 1, 3, 4 and 5** at Screening and End of Treatment visits, and at the time point of the confirmatory CT scan (for complete response/partial response).

12. Archival tumor tissue (FFPE block; or a minimum of two H&E-stained slides plus at least 10 consecutive, unstained, $4 \pm 1 \mu\text{m}$ thick sections, placed on positively charged slides) should be collected at the SV from **all enrolled patients** for biomarker assessment (including PD-L1 testing). If archival tumor tissue is not available, *de novo* biopsy may be performed but only if considered by the Investigator as safe and tolerable for the patient.

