5.3.2.7 Pregnancy testing

Women of child-bearing potential must have a negative hCG at Screening and within 72 hours prior to dosing at C1D1. Subsequently, serum pregnancy testing will be performed prior to study drug dosing on D1 of every cycle, at the End of Treatment visit, and serum or urine pregnancy testing will be performed monthly thereafter for 150 days following the last administration of study treatment.

Pregnancy testing after the end of treatment may be performed at the patient's local gynecologist to reduce the burden related to study visits at the site, but must be communicated to the study Investigator.

The Investigator may conduct additional pregnancy tests (serum or urine) to confirm the absence of pregnancy at any time during the study. If a pregnancy test result is positive, study drug must be discontinued, the patient followed for safety, and the outcomes of the pregnancy assessed (see Section 7.4.5). Further details regarding the risk of pregnancy are provided in Section 7.1.3.

5.3.2.8 *Adverse event monitoring*

AEs will be monitored throughout the study and graded in severity according to the guidelines outlined in NCI CTCAE 5.0.

Please refer to Section 7 for details regarding AE collection and management.

5.3.2.9 *Concomitant medications*

Any medications or significant non-drug therapies (including herbal medicines) that are taken by or administered to the patient during the course of the study (until the safety follow-up visit at Day 28 for all patients, and Day 90 for patients receiving derazantinib-atezolizumab in combination) must be recorded in the eCRF including the dosage, frequency of administration, route of administration, therapeutic indication, and start/stop dates of use.

5.3.3 *Efficacy assessments*

5.3.3.1 *Tumor imaging and assessment of disease*

The process for image collection and transmission to the central imaging vendor is provided in the Imaging Charter. Tumor disease assessments should comprise the chest, abdomen, and pelvis. Tumor imaging should be acquired by computed tomography (CT, strongly preferred). Magnetic resonance imaging (MRI) should be used when CT is contraindicated, and for imaging in the brain.

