7.1.3 Contraception and pregnancy

Derazantinib may have adverse effects on a fetus *in utero*, and may have transient adverse effects on the composition of sperm.

There are no known reproductive risks to the female partner of a male patient receiving atezolizumab.

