7.1.3.1 Contraception

Participants in this study must be informed that taking the study medication may involve unknown risks to the fetus if pregnancy were to occur during the study. In order to be enrolled in the study, both male and female patients of child-producing potential must agree to the contraception requirements in Inclusion criterion 9b) (see Section 4.2), and must comply with these requirements from the day of first study medication, or for oral contraception from 14 days prior to the first study medication, throughout the study period, and until at least 150 days after administration of the last dose of study medication.

If there is any doubt that a patient of child-producing potential will reliably comply with the requirements for contraception, the patient should not be enrolled in the study.

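### The LH/FSH cut-off in footnote 1 of the inclusion criteria points the wrong way, so some recently menstruating women escape mandatory pregnancy testing

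*Protocol*

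**What the plan says.** Protocol Section 4.2 carries two definitions of a woman who cannot become pregnant.

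- **Footnote 1** hangs on the serum hCG item of criterion 8. One of its routes covers a woman under 55 who had spontaneous menses during the last year and is currently amenorrhoeic, "AND with postmenopausal gonadotropin levels (luteinizing hormone and follicle-stimulating hormone levels $<$ 40 IU/L". A low estradiol (below 5 ng/L) and the laboratory's own postmenopausal range follow as alternatives joined by *or*.
- **Footnote 3** hangs on the word *postmenopausal* in criterion 9, which sets the contraception duties. It asks for at least 12 months without menses and no other medical cause. In women under 45, "a high follicle stimulating hormone (FSH) level in the postmenopausal range may be used to confirm a post-menopausal state", provided they use no hormonal contraception or replacement. It adds: "In the absence of 12 months of amenorrhea, a single FSH measurement is not sufficient".

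Pregnancy testing is tied to childbearing potential. Section 5.3.2.7 states: "Women of child-bearing potential must have a negative hCG at Screening and within 72 hours prior to dosing at C1D1". It then requires a test before dosing on Day 1 of every cycle and at End of Treatment. After that, in the words of Table 1 footnote 10, "serum or urine pregnancy testing will be performed monthly for 150 days (5 months) following the last administration of study treatment". Section 7.1.3 gives the reason: "Derazantinib may have adverse effects on a fetus" in utero.

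**The concern.** Footnote 3 shows that the protocol itself regards a high FSH as the postmenopausal sign. Footnote 1 accepts values below 40 IU/L and still calls them postmenopausal. As written, a woman whose gonadotropins are low, and who menstruated within the year, can be declared not of childbearing potential on those values alone.

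The unsafe error falls on women with low gonadotropins, who are wrongly exempted. Women with high values can still qualify through the laboratory-range alternative.

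The same woman remains of child-producing potential under criterion 9, so she owes contraception but no pregnancy test. Contraception does not reveal a pregnancy already present at entry, and a contraceptive failure during treatment could go unnoticed. Section 7.4.5 requires study drug to stop at once on pregnancy, which depends on someone detecting it.

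**Working it through.** The plan states no figure to reproduce. The check sets the two definitions side by side, tries them on example patients, and counts the tests lost.

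**Step 1. The two footnotes (Section 4.2)**

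| | Footnote 1, third route | Footnote 3 |
|---|---|---|
| Attached to | hCG item, criterion 8 | postmenopausal, criterion 9 |
| Amenorrhoea | current; menses within the last year | at least 12 months |
| FSH taken as postmenopausal | below 40 IU/L (with LH) | high |
| Hormones sufficient without 12 months | yes | not a single FSH |
| Other medical cause ruled out | not required | required |

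Because the alternatives in footnote 1 are joined by *or*, the LH/FSH limb is enough by itself.

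**Step 2. Two illustrative women.** The values are invented to exercise the rules. Both are under 55, last menstruated 3 months ago and are now amenorrhoeic without hysterectomy.

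- *LH and FSH both 10 IU/L.* Footnote 1: 10 < 40, so she is not of childbearing potential and no hCG is required. Footnote 3: 3 months is less than 12, so she is not postmenopausal.
- *LH and FSH both 60 IU/L.* Footnote 1: 60 is not below 40, so she fails this limb, although high FSH is what footnote 3 looks for. Footnote 3: still not postmenopausal, because a single FSH does not replace 12 months.

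**Step 3. The same women with the sign reversed to > 40 IU/L**

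- At 10 IU/L she is no longer exempt through this limb, and the footnotes agree.
- At 60 IU/L footnote 1 now exempts her and footnote 3 does not. The conflict over 12 months survives the sign change.

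**Step 4. Tests lost per exempted woman** (Section 5.3.2.7; Table 1 footnote 10), for n cycles started:

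Screening 1 + Day 1 of each cycle n + End of Treatment 1 + monthly tests over 150 days (150/30 = 5) = **n + 7**

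| Cycles started | Weeks of treatment (n × 3) | Tests lost |
|---|---|---|
| 1 | 3 | 1 + 7 = 8 |
| 3 | 9 | 3 + 7 = 10 |
| 9 | 27 | 9 + 7 = 16 |

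Each total falls by one if a single sample serves as both the Screening test and the 72-hour pre-dose test.

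**The case against.** **Reach.** The marker for footnote 1 appears only on the criterion 8 hCG line. Section 5.3.2.7 and Table 1 footnote 10 use the term without citing it, and Section 7.1.3.1 sends the reader to criterion 9. A site that applied criterion 9's definition would test this woman throughout. On that narrow view, footnote 1 directly waives only the Screening test, so the loss is 1 rather than n + 7. It is true that no sentence settles the matter. But footnote 1 is the only text that says who is not of *childbearing* potential, the term used in the testing rules; criterion 9 goes on to define *child-producing* potential. Applying footnote 1 to all the tests is the natural reading, and the ambiguity is itself a reason to merge the two.

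**Safeguards.** Unless another criterion 9 exception applies, she must abstain or use highly effective contraception "until at least 150 days after administration of the last dose of study medication" (Section 7.1.3.1). Exclusion criterion 26 bars patients who are "Pregnant or breast feeding", the Screening visit section links the serum test to that exclusion, and the investigator may add tests. These reduce the risk, but none makes a test mandatory for her.

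**Typing slip or PDF misreading.** The limb speaks of postmenopausal levels, so an alert clinician may notice the contradiction. The character may also have been misread in extraction. The neighbouring signs (age 55 or over, estradiol below 5 ng/L) read sensibly, which lowers that doubt without removing it. Step 3 shows that a conflict remains even if the source reads > 40.

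**Few women.** This is probably right. It limits the importance of the error but does not make the rule correct.

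**Conclusion.** The concern holds: footnote 1 is wrong as written, on the protocol's own text. It takes low LH/FSH as postmenopausal where footnote 3 takes high FSH, and it drops the 12-month requirement that footnote 3 insists on.

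The cost per affected woman is n + 7 required tests (8 to 16 for one to nine cycles), assuming footnote 1 governs every rule that uses the term childbearing potential. On the narrowest reading it is the Screening test alone.

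Affected women are under 55, menstruated within the last year, are now amenorrhoeic without hysterectomy, and are classified on LH/FSH. The documents give no age or sex distribution, so no count is possible, and nothing in them shows that any woman has been exempted. The direction of the sign rests on the PDF reading; the 12-month conflict does not. This should be fixed as a patient-safety matter. It does not touch the error rates, power or any endpoint.

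**What to change.** 1. Check the sign in the source file. If it reads as here, change the limb in footnote 1 to LH and FSH > 40 IU/L.
2. Preferably replace both footnotes with one definition of childbearing potential, keeping footnote 3's 12-month rule. Cite it in criteria 8 and 9, Sections 5.3.2.7 and 7.1.3.1, and Table 1 footnote 10. Reversing the sign alone leaves the conflict shown in Step 3.
3. Identify any enrolled woman exempted from testing on LH/FSH values, and start testing if she does not meet the corrected definition.

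The text change is one character, or slightly more if the definitions are merged, plus a short check of enrolled women. It is still a protocol amendment that must go to the ethics committees under Section 9.5, with up to 100 sites planned. Until approval, Section 5.3.2.7 already lets investigators test at their discretion. No change to sample size, endpoints or analysis is needed.

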4.3 Exclusion criteria

Patients who meet **any** of the following criteria at Screening must not be enrolled in the study (patients may repeat the screening procedures within the screening period after initially failing to comply with exclusion criteria; rescreening for molecular inclusion criteria is not permitted unless the tissue biopsy or liquid biopsy was not evaluable for technical reasons):

Prior cancer treatment

1. Receipt of treatment before the first dose of study drug (Cycle 1 Day 1) within an interval shorter than the following, as applicable:
 - One chemotherapy or biological (e.g., antibody) cycle interval
 - Five half-lives of any small molecule investigational or licensed medicinal product
 - Two weeks, for any investigational medicinal product (IMP) with an unknown half-life
 - Four weeks of curative radiotherapy
 - Seven days of palliative radiotherapy
 - 12 months of neo-adjuvant or adjuvant chemotherapy or radiation (only applies to **Substudy 3**)
2. For **Substudy 3** patients, any prior treatment with anti-PD-1 or anti-PD-L1-therapeutic antibody, or PD-1/PD-L1 pathway-targeting agents
3. Prior FGFR inhibiting treatment (except **Substudy 4**).
4. For **Substudy 4** patients, prior treatment with FGFR inhibitor in combination with anti-PD-1 or anti-PD-L1 therapeutic antibody or PD-1/PD-L1 pathway-targeting agents.

Critical organ impairments

5. Concurrent evidence of clinically significant corneal or retinal disorder likely to increase the risk of eye toxicity, including but not limited to bullous/band keratopathy, keratoconjunctivitis (unless keratoconjunctivitis sicca), corneal abrasion (unless related to trauma), inflammation/ulceration, confirmed by ophthalmological examination.
6. History of clinically significant cardiac disorders:
 - Myocardial infarction, or New York Heart Association Class II to IV congestive heart failure, within 6 months of the first dose of study drug
 - Concurrent and clinically significant abnormalities on ECG at Screening, including QTcF > 450 ms for males or > 460 ms for females (mean values from triplicate ECGs; see Section 5.3.2.4)

7. Serum electrolyte abnormalities defined as follows:
 - Hyperphosphatemia: serum phosphate > institutional ULN
 - Hyperkalemia: serum potassium > institutional ULN
 - Hypokalemia: serum potassium < institutional LLN
 - Hypercalcemia: corrected serum calcium > 3.1 mmol/L (> 12.5 mg/dL)
 - Hypocalcemia: corrected serum calcium < 1.75 mmol/L (< 7.0 mg/dL)
 - Hypomagnesemia: < 0.4 mmol/L (< 0.9 mg/dL)
8. History of major thrombotic and clinically relevant bleeding event in the last 6 months before Screening which in the assessment of the Investigator puts the patient at high risk of bleeding during the study
9. Uncontrolled tumor-related hypercalcemia

Medical history

10. Bellmunt score 3, or 2 if based on a combination of hemoglobin < 10 g/dL and presence of liver metastasis.¹
11. Any unresolved (at the time of Screening) clinically significant CTCAE grade ≥ 2 toxicity (except for alopecia, grade 2 platinum-therapy related neuropathy, grade 2 anemia from previous anti-tumor treatment, grade 2 renal impairment per reduced CLCR by Cockcroft-Gault of 30–60 mL/min [which is generally accepted for this cancer population], and/or medical/surgical procedures/interventions).
12. Known CNS metastases
13. Lack of recovery from major (e.g., open abdominal) surgery after 4 weeks, or major elective surgery is planned during the foreseeable duration of the study
14. Concurrent uncontrolled or active infection with human immunodeficiency virus (known HIV 1/2 antibodies positive)
15. Active hepatitis B or chronic hepatitis B without current antiviral therapy and an HBV DNA ≥ 100 IU/mL
Note: Active hepatitis B is defined as a known positive hepatitis B surface antigen (HBsAg) result.
16. Active hepatitis C
Note: Active hepatitis C is defined by a known positive Hep C antibody result and known quantitative hepatitis C virus (HCV) RNA results greater than the lower limits of detection of the assay.
17. Active tuberculosis
18. Severe bacterial, fungal, viral and/or parasitic infections on therapeutic oral or IV medication at the time of first dose of study drug administration
19. Significant gastrointestinal disorders that could, in the opinion of the Investigator, interfere with the absorption, metabolism, or excretion of derazantinib (e.g., Crohn's

¹ Bellmunt scores (0–3) (Bellmunt 2010) are derived from three adverse risk factors (ECOG PS of ≥ 1 , hemoglobin level < 10 g/dL, and presence of liver metastasis), and are based on the presence of zero, one, two, or three of the prognostic factors.

disease, ulcerative colitis, diarrhea, extensive gastric resection, functionally relevant gastrointestinal obstruction, or vomiting)

20. History of additional malignancy that is progressing or requires active treatment. Exceptions include basal cell carcinoma of the skin, squamous cell carcinoma of the skin that has undergone potentially curative therapy, or *in situ* cervical cancer.

Note: An incidental finding of prostate cancer (identified upon resection of the prostate) is acceptable, provided that the following criteria are met: Stage T2N0M0 or lower; Gleason score ≤ 6 , and prostate-specific antigen below lower limit of normal by local laboratory.

21. Chronic leg ulcers, decubitus ulcers, or unhealed incisions.

General patient disposition

22. Known hypersensitivity or allergy any component of the derazantinib formulation.
23. Unable or unwilling to swallow the complete daily dose of study drug, or contraindicated to receive study drug.
24. Any other uncontrolled intercurrent illness that would unduly increase the risk of toxicity or limit compliance with study requirements, including but not limited to ongoing or active symptomatic infection, uncontrolled diabetes mellitus, or hepatic, renal, respiratory, or psychiatric illness.
25. A history or evidence of psychiatric, substance abuse, or any other clinically significant disorder, condition or disease that, in the opinion of the Investigator or the Sponsor if consulted, would pose a risk to the safety of the patient, or would interfere with the study evaluation, procedures, or completion.
26. Pregnant or breast feeding.

In addition, the following exclusion criteria related to atezolizumab are applicable **only** to patients to be enrolled into **Substudies 3 and 4**:

27. Treatment with systemic corticosteroids (except for steroidal replacement therapy) or other systemic immunosuppressive medications (including but not limited to prednisone, dexamethasone, cyclophosphamide, azathioprine, methotrexate, thalidomide, and anti-tumor necrosis factor agents) within 2 weeks prior to first dose of study drug or anticipated requirement for systemic immunosuppressive medications during the study. Generally, inhaled, intranasal, intraocular, topical, and intra-articular joint injections are allowed.
28. Uncontrolled pleural effusion, pericardial effusion, or ascites requiring recurrent drainage procedures (once monthly or more frequently).
29. History of allogeneic stem cell or solid organ transplantation.
30. History of severe allergic, anaphylactic, or other hypersensitivity reactions to chimeric or humanized antibodies or fusion proteins.
31. Known hypersensitivity or allergy to biopharmaceuticals produced in Chinese hamster ovary cells or any component of the atezolizumab formulation

32. Hypersensitivity to atezolizumab or to any of the excipients
33. Patients requiring systemic treatment within the past 3 months or a documented history of clinically severe autoimmune disease that requires systemic steroids or immunosuppressive agents. (Exceptions include any patient on 10 mg or less of prednisone or equivalent, patients with vitiligo, hypothyroidism stable on hormone replacement, Type I diabetes, Graves' disease, Hashimoto's disease, alopecia areata, eczema)
34. History of idiopathic pulmonary fibrosis (including pneumonitis), drug-induced pneumonitis, organizing pneumonia (i.e., bronchiolitis obliterans, cryptogenic organizing pneumonia), or evidence of active pneumonitis on Screening chest CT scan

